Study Title: A Multidomain Intervention Program for Older People with Dementia

NCT#: NCT04948450

Document Date: October 7, 2022

Document Type: Study Protocol

Protocol Title

A Multidomain Intervention Program for Older People with Dementia

Background

Dementia is a syndrome characterized by cognitive decline interfering with daily function. Alzheimer's disease and vascular dementia are the commonest causes of dementia separately or in combination accounting for over 80% of all dementia cases. Dementia is one of the major causes of disability and dependency among older people worldwide. The number of deaths due to dementia increased by 148% (140–157%) between 1990 and 2016. Dementia has significant social and economic implications in terms of direct medical and social care costs, and the costs of informal care. In 2020, the total global societal cost of dementia was more than 1 trillion USD.

Medications for dementia are considered to be only modestly effective.⁷ The most commonly prescribed drugs are acetylcholinesterase inhibitors (AChEIs), and N-methyl-d-aspartate receptor (NMDAr) antagonists, such as memantine, may improve cognitive and behavioral outcomes, but their clinical impact remains modest and controversial. Many of these pharmacological treatments have been associated with adverse effects and greater risk of contraindications. Currently, no disease-modifying treatments has been demonstrated to be fully effective in controlling the symptoms of dementia. The effect of single-domain trials for people with dementia is still unclear. Some positive benefits have been reported for physical activity-based interventions, cognitive training. However, these benefits are of only borderline clinical relevance, and the overall quality of evidence in relation to most other outcomes was low. Many experts consider that since dementia is a complex, multifactorial disorder multidomain intervention targeting several risk factors and disease mechanisms may be more effective than single interventions to increase cognitive function, increase social activity and reduce depression, delay functional decline, while enhancing the quality of life of caregivers. The multidomain approach in many prevention trials has already proven its efficacy in chronic conditions that are associated with the development of dementia such as type 2 diabetes mellitus and cardiovascular disease. Multidomain interventions have been shown to be effective in improving cognition, reducing neuropsychiatric symptoms and delaying progression of functional impairment or disability in dementia patients in community- dwelling and nursing homes.

In Vietnam, the older adult population is increasing rapidly in both absolute and relative numbers with the average lifespan increasing by four to 75 years in the last two decades. The prevalence of cognitive symptoms of dementia in adults aged 60 years and above is relatively high in Vietnam (14.4–46.4%) with an estimated 2.4 million people living with dementia in Vietnam by 2050.²⁵ Advancing the mental health of older people in Vietnam is critical in the face of population growth and increased living standards resulting in longer lifespan. In the first Vietnam National Dementia Conference, dementia was recognized as a public health priority in Vietnam.²⁶ The number of older people living in nursing homes is increasing in Vietnam, in which the percentage of people with dementia accounts for the majority. However, there was limited evidence on multifactorial intervention program for people with dementia in nursing homes in Vietnam. In order to improve treatment effectiveness, reduce symptoms and improve the quality of life of patients with dementia and their caregivers, we plan to conduct a pilot study to investigate the feasibility of a multidomain intervention program (physical; cognitive; social and management of metabolic and vascular risk factors) for older people with dementia in nursing homes.

Objectives

Primary

To assess the feasibility of a multidomain intervention program (physical, cognitive, social and management of metabolic and vascular risk factors) for older people with dementia in nursing homes.

Secondary

To investigate the effect of a multidomain intervention program on behavioral and psychological symptoms, quality of life, functional ability, falls and sleep, frailty, global cognition and the specific cognitive domains of attention, memory, fluency and executive function; and death rate for older people with dementia.

Method

Trial Design and Participants

This is a two-armed, multicenter, randomized controlled pilot study, based in nursing homes in Hanoi, Vietnam.

Inclusion Criteria

We aim to enroll participants aged over 60 years, living in nursing homes who have a diagnosis of major neurocognitive disorder (according to DSM 5 criteria), stage mild to moderate (according

to Clinical Dementia Rating). Participants receiving pharmacological treatment for dementia must be on a stable dose for at least 3 months prior to the study. Eligible participants must be able to mobilize independently with or without a mobility aid and without physical assistance.

Exclusion Criteria are

- ✓ Acute and malignant diseases (eg, advanced cancers, end-stage chronic diseases, acute myocardial infarction, stroke)
- ✓ Symptomatic cardiovascular disease or coronary revascularization within 1 year
- ✓ Clinical evidence of schizophrenia, severe depression, psychiatric or bipolar disorder (according to DSM-V TR criteria)
- ✓ Alcoholism or substance dependence (according to DSM-5 criteria), currently, or within the past 2 years
- ✓ Severe loss of vision, hearing or communicative ability (according to the interRAI Community Health Assessment)
- ✓ Participant or family unwilling to participate in the study.

Recruitment

Participants will be recruited from November 2022 until December 2023.

Research Team

The research team consists of 5 researchers, 2 research assistants, 2 neurologists and 2 physiotherapy experts. Prior to recruiting participants, the research assistants will complete a training program in screening and data collection using the specific measures to be used in the study.

Sample Size Estimates

Assuming a standardised effect sizes (ES) of 0.2 for a pilot randomised trial, with 90% power and two-sided 5% significance, and allowing for a 10% dropout rate and 5% mortality, the final sample size to be recruited is 60 (30 per study arm).

Randomisation, Concealment, and Allocation

A concealed, computer-generated sequence of randomly permuted blocks (block size = 4), stratified by age (60–69, 70–79, 80 and over) and disease severity (mild or moderate) will be generated by a statistician not otherwise involved in the study. Randomization will occur at the completion of the entire baseline assessment.

Blinding

Participants will be informed that they will be randomly assigned to one of the two treatment groups by the research assistants. Investigators will be blinded to the intervention allocation. All outcome measures will be administered by blinded assessors.

Study Procedure

The study PI and/or researchers in the research team will contact adults aged 60 years and older in the nursing homes (Orihome, Nhan Ai, Dien Hong) to introduce the study. If they are interested in participating, the study PI and/or researchers in the research team will screen them for their eligibility. If they meet the inclusion criteria and are interested in participating, written informed consent will be obtained. Participants will be evaluated for capacity to give informed consent. If participants have the capacity to consent to the research project, they will receive a complete explanation of the purpose, risks, and procedures of the study and sign a written informed consent. Otherwise, a family member will consent for them.

A screening log will be kept to document number and reasons of participants who do not meet the inclusion criteria, decline to participate, or any other reasons.

Participants who agreed to participate in the study will be randomized into two equal groups, to receive either a multidomain intervention (intervention group) or regular health advice (control group). The intervention will include physical, cognitive, and social interventions, and management of metabolic and vascular risk factors.

The patients in the intervention group and the control group will be still participating in the usual care and activity, which were consistent across all three nursing homes in the study. The activities including quizzes and movement games will be held every 3 months. They will also be doing 15-minute morning exercise every day with light intensity. Participants in both the intervention and the control groups will be treated for dementia according to the recommendations of the Vietnam Alzheimer Disease and Neurocognitive Disorders Association.

All participants will meet the study physician to have an examination at baseline, 3 months and 6 months. At each examination, participants will undergo a physical examination, anthropometry (weight, and hip and waist circumference), blood pressure determination, pulse rate and rhythm check, assessment for cardiovascular risk factors and metabolic diseases (smoking, drinking, hypertension, coronary artery disease, dyslipidemia, atherosclerosis, diabetes) and assess blood test results (lipid profile, HbA1C and fasting glucose if patients have diabetes). Blood pressure measurements will be made on the left arm of the seated participants with a

sphygmomanometer and an appropriately sized cuff; the average of 2 physician-obtained measures constitute the examination blood pressure. Metabolic and vascular risk factors will be ascertained by self-report (or caregivers report/nursing home report). Diabetes is defined as fasting glucose >7 mmol/l or use of insulin or oral hypoglycemic medications. Hypertension is defined as a systolic blood pressure of 140 mm Hg or more, or a diastolic blood pressure of 90 mm Hg or more, or taking antihypertensive medication. Dyslipidemia is defined as having an increased level of triglycerides, total cholesterol, or low-density lipoprotein cholesterol (LDL-C) or decreased level of high-density lipoprotein cholesterol (HDL-C). Results will be provided to participants and their doctors.

Interventions

The Intervention Group

In addition to what is given to both groups, the participants in the intervention group will receive three intervention components in 6 months: (1) physical activity; (2) cognitive intervention; and (3) social intervention as well as (4) management of metabolic and vascular risk factors. Physical activity and cognitive stimulation interventions will be performed at separate sessions.

Physical Activity Intervention

Progressive resistance training (PRT) for the physical intervention will be provided at the nursing home for 45 minutes twice a week. The sessions will be organized in groups (10 patients/group) and supervised by 2 physiotherapists. Within each small group (maximum 10) participants will follow the program tailored to their individual functioning level, with constant oversight by trainers.

The exercise program consists of progressive resistance training. Participants will progress through the 6-month intervention, guided by daily ratings of perceived exertion (15–18) on the Borg Scale.

People with dementia and their care staff will be instructed to follow the prescribed PRT exercises for the rest of the week. Participants will be encouraged to exercise daily. Physiotherapists will determine progress subjectively based on the ability of the person with dementia. Training volume will be monitored by adding up the total minutes of participation during each day of the prescribed program.

Cognitive Intervention

The study subjects will receive cognitive intervention based on Cognitive Stimulation Therapy with rehabilitation experts. The intervention involves 14 sessions of themed activities, which typically run twice weekly. The sessions will be organized in groups (6-10 patients/group). Each session lasts about 45 minutes. To make sure that there is continuity between the sessions they will follow the same structure: introduction (10 minutes), main activity (25 minutes) and conclusion (10 minutes). A total set of 14 exercises will be selected including physical games, sounds, childhood, food, current affairs, word association, being creative, categorising objects, orientation, using money, number game, word games, team quiz, which will be culturally adapted in Vietnam. Necessary activities related to daily lives will also be included. People with dementia and their care staff will be instructed on how to practice the various activities at their nursing home for the rest of the week in a separate room. Training volume (multiplying the number of repetitions performed/day by the number of days) will be monitored using a training diary.

Social Intervention

Social intervention will be combined with physical and cognitive interventions through doing these interventions in a group, ie, playing group games during exercises (eg, dancing, throwing ball to each other) or doing cognitive stimulation therapy in a group.

Management of Metabolic and Vascular Risk Factors

In the intervention group, metabolic and vascular risk factors will be evaluated by cardiologists and endocrinologists in the study.

Study physicians will assess change in blood pressure, weight and BMI, and hip and waist circumference, blood tests (glucose, lipid parameters, fasting glucose and HbA1C if the person with dementia has diabetes) at 3 and 6 months.

Participants in the intervention group will be provided with information on the importance of reducing risk factors, guidance on lifestyle changes and prescribing treatment if necessary by the cardiologists and endocrinologists. The target for blood pressure is less than 120/90 mmHg and the target for HbA1c is less than 8%.

The Control Group

The control group will receive general health advice every 3 months based on their physical examination and blood findings. They will be provided usual care plus health education materials.

Outcome Measurements

- Primary Outcome

The primary outcome of the study is the feasibility of the intervention which will be assessed via the adherence and retention in intervention group.

Adherence: a count of sessions (percentage) attended out of the total planned

Retention: the number (percentage) of participants in each group who did not discontinue the study.

➤ Secondary Outcomes

Cognitive Function

Global cognition will be measured by Alzheimer's Disease Assessment Scale-Cognitive (ADAS-Cog), the Clinical Dementia Rating scale (CDR); executive function by the Clock test; and attention by digit span forward and digit span backward

Behavioral and Psychological Symptoms of Dementia (BPSD)

Researchers will interview care staff using the Neuropsychiatric Inventory (NPI) questionnaire.

Higher scores indicating greater severity

Functional ability will be assessed by using the Activities of Daily Living Scale (ADL), the Instrumental Activities of Daily Living Scale (IADL), handgrip strength and a 30 s chair stand test (30 s CST). The 30 s CST consists of counting the number of sit-stand-sit cycles completed during the 30 s test

Falls

Falls will be assessed by the fall incident report at baseline and during the study period.

Sleep Problem

Sleep Problem will be assessed with the Pittsburgh Sleep Quality Index. A global PSQI score over 5 indicates poor sleep

Health-Related Quality of Life

Health-related quality of life will be assessed with the Quality of Life in Alzheimer's Disease scale (QoL-AD). Total scores range from 13 to 52 with higher scores indicating higher quality of life.

Death

Death will be assessed through caregiver reports or nursing home records.

Ethical Approval and Consent

Ethical approval has been performed in accordance with the Declaration of Helsinki and have been approved from the National Geriatric Hospital (1139/IRB) on October 7, 2022. Participants will be evaluated for capacity to give informed consent. If participants have the capacity to consent

to the research project, they will receive a complete explanation of the purpose, risks, and procedures of the study and sign a written informed consent. Otherwise, a family member will consent for them. The trial is registered with ClinicalTrials.gov identifier: NCT04948450 registered on 02/07/2021.

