#### **Estimation of Treatment Effects**

##### *Continuous outcomes*

To investigate the treatment effects on continuous outcomes, we utilized Linear Mixed-effects Model (LMM) with random slopes. The treatment effects were estimated by modeling the interaction between time ( $T$ : after vs. before intervention) and the treatment arms ( $A$ : treatment vs. control). The specification of the models is provided below:

$$Y_{ij} = (\beta_0 + b_{0i}) + (\beta_1 + b_{1i}) * T_{ij} + \beta_2 T_{ij}^* A_i + \varepsilon_{ij}$$

Where:

$Y_{ij}|T, A, b_i \sim N(\mu, \sigma_y^2)$  is the study outcome of  $i^{th}$  individual at  $j^{th}$  measurement

$\beta_2$  is the treatment effect of interest

$b_i = (b_{0i}, b_{1i})' \sim N(0, D)$  are random intercepts and random slopes, respectively, with  $D$  unstructured variance-covariance matrix

$\varepsilon_{ij} \sim N(0, \Sigma)$  are the random errors, with  $\Sigma$  compound symmetry variance-covariance matrix

We constrained the baseline values of the outcome to be the same between the two arms in the model by omitting the group main effect (i.e., main effect of  $A$ ). This procedure is to gain efficiency of the model and is valid under randomization.

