##### *Binary outcomes*

For binary outcomes, the Generalized Estimating Equation models (GEE) were applied as our causal effects of interest are the population-average effects. The log link function was utilized to obtain the RR estimates. The specification of the models is provided below:

$$Y_{ij} \sim Bernoulli(\pi_{ij})$$

$$\log(\pi_{ij}) = \gamma_0 + \gamma_1 T_{ij} + \gamma_2 T_{ij}^* A_i$$

Where:  $\gamma_2$  represents the treatment effect of interest. We specified the exchangeable working assumption and obtained the empirical standard errors. The same constraint for baseline values, as mentioned in the LMMs, was applied.

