### **Handling missing values**

We applied direct likelihood method, which is valid under LMM, to address missing values for continuous outcome models.

For binary outcomes models, the Multiple Imputation by Chained Equations (MICE) method was employed. This algorithm created multiple imputed datasets based on a set of imputation models, assuming missing at random. We utilized logistic regressions as the imputation models for binary outcomes. The imputed model included the outcome variable and candidate predictors, including age, sex, marital status, education, and BMI. Due to small sample size, we could not impute all outcomes in the same model, therefore, each outcome was imputed separately. In total, 20 imputed datasets were created for each outcome. The estimates were estimated in each imputed dataset and then were pooled to obtain the single estimate based on Rubin's rules. We also compare the estimates based on multiple imputation to the results of available-case analyses.

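### The mixed model for continuous secondary outcomes omits the randomisation strata; adding them is a cheap, minor improvement that helps only if they predict follow-up well beyond baseline

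*Protocol*

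**What the plan says.** Protocol, Randomisation, Concealment, and Allocation: permuted blocks of 4, "stratified by age (60–69, 70–79, 80 and over) and disease severity (mild or moderate". That is 3 × 2 = 6 strata for 60 participants.

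SAP, Continuous outcomes: "The treatment effects were estimated by modeling the interaction between time" and arm. The model equation has an intercept, time, time-by-arm, a random intercept and a random slope. The arm main effect is left out: "We constrained the baseline values of the outcome to be the same between the two arms". The stated reason is efficiency.

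SAP, Handling missing values: age appears as one of the "candidate predictors, including age, sex, marital status, education, and BMI" in the imputation of binary outcomes. Severity appears nowhere in the SAP text available for review. Part of the SAP was removed before review, so this describes only the text that could be read.

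Protocol, Outcome Measurements: the primary outcome is feasibility (adherence and retention). The outcomes that go through the mixed model are secondary.

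**The concern.** Stratified blocks limit chance imbalance between arms on age and severity, so the treatment estimate varies less from trial to trial than under simple randomisation. A model without the strata does not credit this. It leaves their variation in the residual, and its standard error can exceed the true sampling variability. Intervals for ADAS-Cog, NPI, QoL-AD and the functional scores would then be wider than the design justifies, and tests somewhat conservative.

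The constrained baseline limits the effect. It makes the estimate conditional on the baseline score, so only what the strata add beyond that score matters.

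**Working it through.** **Inputs from the documents.** 60 recruited, equal arms, 6 strata, blocks of 4, and "allowing for a 10% dropout rate and 5% mortality". Evaluable: 60 × (1 − 0.15) = 51.

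**The plan's own figure.** The total of 60 does not follow from the stated inputs: an effect of 0.2 with 90% power and two-sided 5% needs 526 per arm. That is a separate matter and does not bear on this point.

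**Assumed, because the documents are silent.** Within-stratum SD 1; baseline to follow-up correlation 0.6; severity split 50/50; severity gap 1 SD at baseline; age bands 20/35/45% with 0.2 SD per band at both visits; loss at random; one follow-up measurement, as in the SAP's before/after coding of time. The severity gap at follow-up is varied.

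**Formula.** With one baseline and one follow-up, the constrained-baseline estimate is in effect analysis of covariance. Let g0 and g1 be the severity gaps at baseline and follow-up. The age-band score (0, 1, 2) has variance 0.35 + 4 × 0.45 − 1.25² = 0.5875, so age adds 0.04 × 0.5875 = 0.0235 to each variance and to the covariance.

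- V0 = 1 + g0²/4 + 0.0235
- V1 = 1 + g1²/4 + 0.0235
- C = 0.6 + g0·g1/4 + 0.0235
- Residual variance without strata: R = V1 − C²/V0
- Residual variance with strata: 1 − 0.6² = 0.64
- Residual SD ratio: √(R/0.64); partial R² of the strata: 1 − 0.64/R

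**Worked case, g0 = 1, g1 = 1.5.** V0 = 1.2735, V1 = 1.5860, C = 0.9985. R = 1.5860 − 0.9970/1.2735 = 0.8031. SD ratio √(0.8031/0.64) = 1.120; partial R² 0.20. Fitting the extra terms costs about 1% (last step), which leaves about 1.11.

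**All cases.** The last column is from simulation: 6,000 null trials per case, stratified blocks, 9 of 60 lost, Kenward-Roger.

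| Severity gap at follow-up (1 SD at baseline) | R | Partial R² | SD ratio | Simulated interval width, without / with strata |
|---|---|---|---|---|
| 0.3 SD | 0.663 | 0.03 | 1.018 | 1.01 |
| 0.6 SD (age effect 0.12 per band at follow-up) | 0.640 | 0 | 1.000 | 0.99 |
| 0.8 SD | 0.651 | 0.02 | 1.009 | 1.00 |
| 1.0 SD | 0.674 | 0.05 | 1.027 | 1.02 |
| 1.2 SD | 0.714 | 0.10 | 1.056 | 1.05 |
| 1.5 SD | 0.803 | 0.20 | 1.120 | 1.11 |

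With no stratum effect at either visit, the simulated width ratio is 0.99. The 0.6 SD row shows that predicting change is not enough: the gap shrinks exactly as the correlation implies, so the strata add nothing to the baseline score.

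**Standard error against actual variability, model without strata.** At 1.2 SD the Kenward-Roger standard error is 0.238 against an empirical SD of 0.230; at 1.5 SD it is 0.254 against 0.237. At gaps of 0.3, 0.8 and 1.0 SD the two are about equal. Most of the excess width is therefore an overstated standard error. The estimate itself is about 1.5% less precise at 1.2 SD and 4% less precise at 1.5 SD (0.237 against 0.228 with strata), with no loss in the other cases.

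**Type I error at 1.5 SD.** Without strata it was 3.5-3.8% in repeated analysis-of-covariance simulations with a t reference, and 4.1% by REML with a normal reference. With strata and a t reference it was 5.4-5.5%.

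**Bias.** At most 0.008 SD in a separate simulation (correlation 0.7, partial R² up to about 0.26).

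**Power at 0.2, Kenward-Roger, without → with strata.** No stratum effect 13.7% → 13.2%; 1.2 SD 11.9% → 13.6%; 1.5 SD 10.4% → 13.9%. With a normal reference, the values run from 12.2% to 15.9%.

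**Cost and break-even.** If the strata predict nothing, the 95% half-width goes from 0.453 to 0.457, a ratio of 0.99. Break-even is a partial R² of 1 − 0.99² = 0.02 on these figures. The separate simulation put it at about 0.04.

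**The case against.** The strongest case is that nothing is wrong. The estimate is unbiased, the SAP already conditions on baseline and says why, and the SAP itself cites the small sample as a limit on model complexity. A visible gain needs a severity gap that at least persists at 1 SD, and real loss of precision appears only if it widens to 1.2 SD or more. The same assumed gap stands in for outcomes as different as NPI and ADAS-Cog. Most of this stands. It is why the point is an optional improvement and not an error, and why its size is given as a range.

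Four stronger readings are tempting but not supported.

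- **Any prediction beyond baseline makes the standard error too large.** It does not. At follow-up gaps of 0.3, 0.8 and 1.0 SD the strata do predict follow-up, yet the standard error and the actual variability are about equal.
- **The omission inflates type I error.** REML with a normal reference gave up to 6.5%, but that comes from the reference distribution; adding the strata under the same reference gave 5.6-6.6%. The SAP text available names no reference distribution. With a t reference, omitting the strata makes the test conservative when it matters at all.
- **The binary-outcome model needs the same change.** It too omits the strata: "We specified the exchangeable working assumption and obtained the empirical standard errors". Its available simulation used observed cases, whereas the SAP specifies multiple imputation. Adding the stratum terms there gave no valid fit in 16% of replicates. No change is supported.
- **Adjustment would rescue power.** The protocol's figure is "Assuming a standardised effect sizes (ES) of 0.2 for a pilot randomised trial", and at that effect power is low with or without the strata.

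**Conclusion.** The point holds as a minor, cheap improvement to the analysis of continuous secondary outcomes. The omission itself is plain in the SAP text available. Its consequence depends on how well age band and severity predict each follow-up score given the baseline score, which the documents do not report. Under the assumptions listed, the specified model gives intervals between about 1% narrower and 11% wider than the stratum-adjusted model. The widest case needs a severity gap that grows by half over the trial. The treatment estimate is not biased, the primary feasibility outcome is not touched, and the change would not make an effect of 0.2 detectable.

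**What to change.** In the mixed model for continuous secondary outcomes, add age band and severity as recorded at randomisation, each with its time interaction. Use main effects of the two factors, not six cells, some of which may be very small. State a small-sample method such as Kenward-Roger, because six fixed effects are added (three main effects, three time interactions) with about 51 evaluable participants.

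For CDR, add age band and its time interaction only: participants are "stage mild to moderate (according to Clinical Dementia Rating), so the severity stratum is itself the CDR stage.

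Leave the model for binary outcomes as specified.

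The SAP is written in the past tense. If the analyses are complete, keep the specified mixed model as the reported analysis and add the stratum-adjusted fit as a labelled post hoc sensitivity analysis.

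The cost is a few lines of SAP text or one re-fit per outcome. The strata are already held from randomisation, so no new data are needed. The downside is about 1% of interval width where the strata turn out not to be prognostic.

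### Only the intervention arm is treated in groups, but both effect models treat participants as independent, so intervals for the secondary effects are too narrow if outcomes correlate within therapy group

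*Protocol*

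**What the plan says.** **Delivery.** On exercise, the Protocol (Physical Activity Intervention) says "The sessions will be organized in groups (10 patients/group) and supervised by 2 physiotherapists", and the same section makes 10 the maximum. On cognitive stimulation (Cognitive Intervention) it says "The sessions will be organized in groups (6-10 patients/group". Under Social Intervention, the social component consists of doing these activities together, so grouping is part of the treatment. Under The Control Group, controls receive usual care, education materials and advice based on their own examination and blood results. No control therapy groups are described.

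**Design.** "This is a two-armed, multicenter, randomized controlled pilot study". Participants are randomised individually, stratified by age band and severity. Three homes take part, and home is not a stratification factor.

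**Analysis.** For continuous outcomes the SAP says "we utilized Linear Mixed-effects Model (LMM) with random slopes". The random intercept and slope are indexed by participant, and the treatment effect is β₂. For binary outcomes it specifies a log-link GEE with an exchangeable working correlation and empirical standard errors, indexed in the same way, with treatment effect γ₂. Neither model has a term or level for therapy group. The only sensitivity analysis stated, under Handling missing values, compares multiple imputation with available cases.

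**The concern.** This is a partially nested design: individuals are randomised, but treatment then creates clusters in one arm only. Members of a therapy group share sessions, trainers and one another's company for six months, so their outcomes may move together. If they do, the intervention-arm mean varies more than the models assume. The standard errors of β₂ and γ₂ are then too small, intervals cover less than 95%, and p-values are too low.

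The GEE's empirical standard errors do not protect against this if the cluster is the participant, as the SAP's notation implies. They then allow for correlation within a participant but not between participants.

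At stake are the treatment-effect estimates under the secondary objective: cognition, behaviour, function, sleep, quality of life and the rest. Anyone who used those intervals to judge promise or to plan further work would take them as more precise than they are.

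**Working it through.** **Plan's own figures.** There is no ICC, design effect or other clustering allowance to reproduce. The Sample Size Estimates section gives only the total: "the final sample size to be recruited is 60 (30 per study arm". That total does not follow from its stated inputs: 2 × (1.960 + 1.282)² / 0.2² gives 526 per arm before losses. That is a separate matter; 30 per arm is used here only to count groups.

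**Inputs.**
- Intervention arm: 30 participants (Protocol, Sample Size Estimates).
- Group size m: 10 for exercise, so 30/10 = 3 groups; 6 to 10 for cognitive sessions, so 3 to 5 groups.
- Losses: 10% dropout plus 5% mortality, so 30 × 0.85 = 25.5 evaluable per arm and 25.5/3 = 8.5 per exercise group.
- ICC: not in the documents; 0.02, 0.05 and 0.10 are assumed.

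**Formulas** (equal arms, equal variances, clustering in one arm only).
- Design effect in the intervention arm: DE = 1 + (m − 1) × ICC
- Standard-error factor for the arm difference: F = √((1 + DE)/2)
- True error of a nominal 5% test: 2 × (1 − Φ(1.96/F))

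For example, with m = 10 and ICC = 0.05: DE = 1 + 9 × 0.05 = 1.45; F = √(2.45/2) = 1.107; 1.96/1.107 = 1.771; true error 7.7%.

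| m | ICC | DE | F | True error | Coverage |
|---|---|---|---|---|---|
| 6 | 0.02 | 1.10 | 1.02 | 5.6% | 94.4% |
| 6 | 0.05 | 1.25 | 1.06 | 6.5% | 93.5% |
| 6 | 0.10 | 1.50 | 1.12 | 8.0% | 92.0% |
| 8.5 | 0.02 | 1.15 | 1.04 | 5.9% | 94.1% |
| 8.5 | 0.05 | 1.375 | 1.09 | 7.2% | 92.8% |
| 8.5 | 0.10 | 1.75 | 1.17 | 9.5% | 90.5% |
| 10 | 0.02 | 1.18 | 1.04 | 6.0% | 94.0% |
| 10 | 0.05 | 1.45 | 1.11 | 7.7% | 92.3% |
| 10 | 0.10 | 1.90 | 1.20 | 10.4% | 89.6% |

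**Check by simulation.** Each scenario had 20,000 runs: 60 people in three homes, individual randomisation, 15% loss, one therapy group per home, and a two-group comparison of means standing in for the mixed model. Ignoring the group effect gave true errors of 5.7%, 7.3% and 10.1% at ICC 0.02, 0.05 and 0.10. At 0.05 the true standard error was 0.307 against a model value of 0.278, a ratio of 1.10.

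**Nursing home, tested separately in the same simulation.**
- A home effect shared by both arms and left out of the model gave true errors of 4.9%, 5.1% and 4.7% at home ICC 0.05, 0.10 and 0.20. There is no inflation.
- With a therapy-group effect present, adding home as a fixed effect left 7.1% at ICC 0.05 and 10.0% at 0.10. It repairs almost nothing.

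**The case against.** **The ICC is unknown, so narrowness is not proven.** This stands. The size of the problem, outcome by outcome, cannot be read from the documents, and it may be negligible for some, such as death. The 10.4% figure needs both the largest group size and the highest assumed ICC. The direction does not depend on the value, however: any positive within-group correlation makes the standard error too small.

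**Three to five groups cannot support a random group effect.** Also true, and a reason not to fit one. Inflating the standard error at stated ICCs requires no such estimate.

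**Any fixed ICC is arbitrary.** It is. With m = 10, a correction at 0.05 (F = 1.107) has a true error of 2 × (1 − Φ(1.96 × 1.107)) = 3.0% if the ICC is zero. It has 2 × (1 − Φ(1.96 × 1.107/1.204)) = 7.2% if the ICC is 0.10. That argues for showing a range, with no value preferred, and for not replacing the main analysis.

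**Treatment effects are secondary in a pilot.** Correct: the primary outcome is adherence and retention. This limits the seriousness, but the SAP still defines formal effect parameters for the secondary outcomes.

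**A stronger reading concerns nursing home.** A reader might infer that a multicentre trial whose models leave out home must have intervals that are too narrow for that reason as well. The documents do not support this. Randomisation is individual, so a home effect common to both arms does not shrink the standard error of their difference. Leaving it out costs precision at most. Adding home with its time interaction would put four more parameters into a log-link GEE that has three, and would leave the group problem in place.

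**Conclusion.** The point holds conditionally. The models have no level for the grouping that the intervention creates, so if outcomes correlate positively within therapy group, the intervals for the secondary effects are too narrow. Over assumed ICCs of 0.02 to 0.10 the standard error is understated by about 4% to 20% with 10 per group and 2% to 12% with 6 per group.

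These figures assume roughly equal arms, equal outcome variances and no clustering in controls. The ICC is that of the quantity β₂ or γ₂ compares. For γ₂ the factor is a rougher approximation, because the two arms' variances differ when their risks differ. One portion of the SAP was not available to this review; the models themselves are written out in full.

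The documents do not support saying that every secondary interval is certainly too narrow, that leaving out nursing home contributes, or that the primary result needs this correction. It is worth acting on because the remedy is cheap.

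**What to change.** Keep the existing models as the main analysis and add to the SAP:

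1. Record each intervention participant's exercise group and cognitive group.
2. For each secondary treatment effect, multiply the standard error of β₂ or γ₂ by √((1 + [1 + (m − 1) × ICC])/2). For binary outcomes, do this after Rubin pooling.
3. Use the observed average group size for m, shown separately for exercise and cognitive groups if they differ, and ICC values of 0, 0.02, 0.05 and 0.10.
4. Report which conclusions change over that range. Do not estimate the group variance from 3 to 5 groups.

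Do not add nursing home as a remedy for narrow intervals. The SAP is written in the past tense; if the analysis is already complete, report this as a labelled sensitivity analysis added afterwards.

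**Cost.** Recording group membership and one paragraph of SAP text. The adjusted intervals are wider, and conservative if the true ICC is near zero. Power falls: for an illustrative standardised effect of 0.8 with 25.5 per arm, the independence standard error is √(2/25.5) = 0.280 and power is Φ(0.8/0.280 − 1.96), about 82%. With m = 8.5 and ICC 0.05 the standard error is 0.280 × 1.090 = 0.305 and power is Φ(0.8/0.305 − 1.96), about 75%. If the ICC really is 0.05, the higher figure was never available at a true 5% error rate.
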